8.4. Pharmacokinetic Statistical Analyses

Dose-proportionality of plasma ALXN1850 PK parameters, C_{max} , AUC_{168h} , AUC_{inf} , (IV dose only), and AUC_{tau} (SC dose only) for both IV and SC treatments over the dose range tested will be investigated. A power model will be fitted to describe the relationship between Y (C_{max} , AUC_{168h} , AUC_{inf} , and AUC_{tau}) and X (dose) using the least squares linear regression model:

• $ln(Y) = ln(\alpha) + \beta ln(X)$, which is the logarithmic form of $Y = \alpha X^{\beta}$, where Y is PK parameter and X is dose.

The intercept of regression line, α , and the slope of the regression line, β , will be presented along with the 90% confidence interval (CI) of the slope. Dose proportionality will be concluded when the 90% CI of the slope (beta) lies entirely within $[(1+\ln(0.8)/\ln(r), 1+\ln(1.25)/\ln(r))]$, where r is the dose range (highest dose/lowest dose).

Dose-proportionality of plasma ALXN1850 PK parameters, C_{max}, AUC_{168h}, AUC_{inf}, (IV dose only), a nd AUC_{tau} (SC dose only) for both IV and SC treatments over the dose range tested will be investigated based on ADA status (ADA negative and ADA positive, and/or pre-existing immunogenicity, treatment-emergent ADA responses, and treatment-boosted ADA responses if data permits) usi ng a similar model.

Absolute bioavailability of ALXN1850 following SC administration will be assessed by comparing AUC_{tau} values of the first SC dose versus AUC_{inf} of the IV dose for the similar dose

cohorts. Log-transformed AUC_{tau} and AUC_{inf} estimates will be analyzed using an analysis of variance model with group (IV vs SC) as a factor. The parameter estimates results will be exponentiated and the ratio of geometric means and 90% CIs will be presented. Analysis will be repeated by ADA status.

9. Safety Analysis

All safety summaries and analyses will be based upon the Safety Set.

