2.3.3. Overall Benefit Risk Conclusion

This is the first time that ALXN1850 will be administered to humans. Because of the potential for immunogenicity, this study will enroll adults with HPP who are not anticipated to require continued treatment with ERT, based on their signs and symptoms, and the Investigator's clinical assessment of their current condition.

Page 33 of 97
Alexion Confidential

This study has been designed to minimize the identified potential risks to participants; there are strict inclusion/exclusion criteria with a robust safety monitoring and risk mitigation plan in place. A SRC will evaluate the available study data at prespecified time points for participant safety and make recommendations on dose escalation, dose modification, or termination of the study. There is no added medical benefit for the participants.

Page 34 of 97	
Alexion Confidential	

OBJECTIVES AND ENDPOINTS 3.

The study objectives and corresponding endpoints are presented in Table 4.

Table 4: **Objectives and Endpoints**

Objective	Endpoints
Primary	
Assess the safety and tolerability of ALXN1850 given IV as a single dose and given SC in 3 qw doses	Incidence of TEAEs and TESAEs
Secondary	
Assess the PK of single IV and 3 SC doses of ALXN1850	ALXN1850 PK (activity) over time profiles and PK parameters
Assess the absolute bioavailability of ALXN1850 SC	AUC _{tau} values of the first SC versus IV administration
Assess the PD effects of single IV and 3 SC doses of ALXN1850	Absolute change and percent change from baseline in plasma concentrations of PPi and PLP and PLP/PL ratio over time
Assess the immunogenicity potential of ALXN1850	Incidence of ADAs and NAbs
Exploratory	
Explore role of ALXN1850 on calcium and bone homeostasis and other PD biomarkers	Absolute, change, and percent change from baseline in ionized Ca, phosphorus, magnesium, PTH, CTX-1 (sCTX), P1NP, osteocalcin, and PA over time
Abbreviations: ADA = antidrug antibody; AUC _{tau} = area u	inder the plasma concentration versus time curve within
the dosing interval; Ca = calcium; IV = intravenous; NA of type I procollagen; PA = pyridoxic acid; PD = pharm	

PL = pyridoxal; PLP = pyridoxal-5'-phosphate; PPi = inorganic pyrophosphate; PTH = parathyroid hormone; qw = weekly; SC = subcutaneous; CTX-1 (sCTX) = serum Ctelopeptide cross-link of type 1 collagen;

TEAE = treatment emergent adverse event; TESAE = treatment emergent serious adverse event

Page 35 of 97	
Alexion Confidential	

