Assess the safety and tolerability of	Incidence of TEAEs and TESAEs
ALXN1850 given IV as a single dose and	
given SC 1 dose per week for 3 weeks	
Secondary	
Assess the PK of single IV and multiple SC	ALXN1850 PK (activity) over time profiles
doses of ALXN1850	and PK parameters
Assess the absolute bioavailability of	AUC _{tau} values of the first SC versus IV
ALXN1850 SC	administration
Assess the PD effects of single IV and	Absolute change and percent change from
multiple SC doses of ALXN1850	baseline in plasma concentrations of PPi and
	PLP and PLP/PL ratio over time
Assess the immunogenicity potential of	Incidence of ADAs and NAbs
ALXN1850	
Exploratory	
Explore role of ALXN1850 on calcium and	Absolute, change, and percent change from
bone homeostasis and other PD biomarkers	baseline in ionized Ca, phosphorus,
	magnesium, PTH, CTX-1 (sCTX), P1NP,
	osteocalcin, and PA over time

Abbreviations: ADA = antidrug antibody; AUC_{tau} = area under the plasma concentration versus time curve within the dosing interval; Ca = calcium; IV = intravenous; NAb = neutralizing antibody; P1NP = N-terminal propeptide of type I procollagen; PA = pyridoxic acid; PD = pharmacodynamics(s); PK = pharmacokinetic(s);

PL = pyridoxal; PLP = pyridoxal-5'-phosphate; PPi = inorganic pyrophosphate; PTH = parathyroid hormone;

SC = subcutaneous; CTX-1 (sCTX) = serum C-telopeptide cross-link of type 1 collagen;

TEAE = treatment-emergent adverse event; TESAE = treatment-emergent serious adverse event

3. Study Design

This is an open-label, dose-escalating study to assess safety, tolerability, PK, PD, bioavailability, and immunogenicity of ALXN1850 when given IV and SC to adults with HPP.

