Individual plasma concentrations of ALXN1850 for each treatment will be presented in data listings and summarized separately using descriptive statistics (N, n [non-missing values within the population], arithmetic mean, SD, %CV, median, minimum, and maximum) by cohort, study day, and scheduled time point. All participants (first and subsequent) will be summarized together for Days 1-8 (predose) for each cohort, after Day 8 only subsequent participants data will be summarized and whereas first participant data will be presented separately. An additional sensitivity analysis will be performed by combining subsequent participants with the first participant (following each SC dosing, ie, SC Dose 1, SC Dose 2, and SC Dose 3) whe re data (corrected from prior carryover exposure post IV dose) is summarized by cohort and scheduled timepoints relative to each dose.

Individual plasma concentrations for ALXN1850 will be plotted for each participant by actual time on both linear and semi-logarithmic scales. Mean plasma concentrations of ALXN1850 versus nominal time will be plotted for each treatment on both linear and semi-logarithmic scales. In addition, mean plasma concentrations of ALXN1850 versus nominal time will be plotted for each treatment by ADA status on both linear and semi-logarithmic scales. The definition of ADA status (ADA negative and ADA positive, and/or pre-existing immunogenicity, treatment-emergent ADA responses, and treatment-boosted ADA responses if data permits, the definition for the ADA response categories is described in the Section 11 of Immunogenicity Analysis).

Individual and mean plasma trough concentrations (C_{trough}) for ALXN1850 versus day following subcutaneous dose administration will be plotted on both linear and semi-logarithmic scales. Time to reach steady state will be graphically assessed by plotting mean plasma C_{trough} concentration versus study day in both linear and semilogarithmic scales.

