8.3. Plasma Pharmacokinetic Parameters

The plasma concentration-time data for ALXN1850 will be analyzed by non-compartmental analysis using Phoenix® WinNonlin® Version 8.0 or higher (Certara USA, Inc., Princeton, New Jersey). The following PK parameters will be derived for ALXN1850 based on actual date and times calculated relative to the actual date and time from the start of dose administration (for example, start of infusion) in each dosing period, where data permit. If missing actual sampling dates and times, then the nominal time relative to the start time of the administration will be used.

C _{max}	Maximum observed plasma concentration
C _{max_corrected}	Maximum observed plasma concentration (for SC dose only if carryover from IV exposure is observed)
C _{trough}	Trough (predose) concentration observed at the start of the dosing interval (C _{trough})
T _{max}	Time of maximum observed concentration
AUCt	Area under the curve (AUC) from time 0 to the last quantifiable concentration, calculated using the linear trapezoidal rule
AUC _{168h}	Area under the curve (AUC) from time 0 to 168h, calculated using the linear trapezoidal rule (for IV dose only)
AUC _{inf}	AUC from time 0 extrapolated to infinity, calculated using the linear trapezoidal method (IV dose only)
AUC _{tau}	AUC within the dosing interval, calculated using the linear trapezoidal method (SC dose only)
AUC _{tau_corrected}	AUC within the dosing interval, calculated using the linear trapezoidal method (for SC dose only if carryover from IV exposure is observed)
t _{1/2}	Apparent terminal elimination half-life, calculated as: ln (2) / Kel
CL	Total body clearance calculated as: Dose / AUC _{inf} (For IV dose only)
CL/F	Apparent total body clearance calculated as: Dose / AUC _{tau} at steady state (For SC dose and only if C _{trough} can attain steady state)
V_d	Volume of distribution during the terminal phase, calculated as: Dose / $[\lambda_z * AUC_{inf}]$ (For IV dose only)
V _d /F	Apparent volume of distribution during the terminal phase, calculated as: Dose / [λ_z * AUC _{tau} at steady state] (For SC dose and only if C _{trough} can attain steady state)
R	Subcutaneous accumulation ratio (AUC _{tau_SC} 3rd dose / AUC _{tau_SC} 1st dose)
F	Absolute bioavailability after subcutaneous administration, $F = AUC_{tau}$ (SC) / AUC_{inf} (IV)

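### The SAP's bioavailability ratio leaves IV carryover in the SC numerator and sets a one-week SC area against an infinite IV area, so its error has no fixed sign and differs between first and subsequent participants

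*SAP*

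**What the plan says.** The endpoint for absolute bioavailability in Protocol section 3, Table 4 is "AUC _{tau} values of the first SC versus IV administration". SAP Table 1 repeats it. Protocol 9.4.3.1 lists F without a formula.

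SAP 8.3 supplies one: "Absolute bioavailability after subcutaneous administration, $F = AUC_{tau}$ (SC) / AUC_{inf} (IV"). It gives no dose number. SAP 8.4 does, "comparing AUC_{tau} values of the first SC dose versus AUC_{inf} of the IV dose", and analyses the log areas in an ANOVA with IV versus SC as the factor, reporting a ratio of geometric means with a 90% CI.

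SAP 8.3 derives two further areas. AUCtau_corrected is planned "for SC dose only if carryover from IV exposure is observed", with no subtraction method written. AUC168h is defined for the IV dose only, and SAP 8.4 uses it only for dose proportionality. The one other carryover correction, in SAP 8.2, is a sensitivity summary of concentrations.

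Two further rules touch F without naming it. SAP 8.3 withholds summaries of AUCinf, CL and Vd when more than 20% of AUCinf is extrapolated. SAP 8.2 says of concentrations that "after Day 8 only subsequent participants data will be summarized and whereas first participant data will be presented separately".

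**The concern.** The first SC dose follows the IV dose by 7 days in most participants and by 14 days in the first participant of each cohort (Protocol Table 3). If IV drug is still circulating, an uncorrected first-dose SC area contains some of it, and contains more after the shorter gap. Separately, drug from the SC dose that circulates after 168 hours is left out of the numerator, while the denominator counts IV drug to infinity. One formula therefore carries a different error in the two groups, and nothing in SAP 8.4 says whether or how they are combined.

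Absolute bioavailability is a secondary objective, and Protocol 4.2 gives it as the reason for the IV dose. No hypothesis test is at stake. What is at stake is whether the reported F and its 90% CI can be read as bioavailability.

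**Working it through.** The documents report no value of F to reproduce, so the check is an illustration under stated assumptions.

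**Inputs**
- Linear one-compartment kinetics, IV bolus, first-order SC absorption (assumption).
- True F 0.75, the planning value in Protocol 4.3.
- Gap: 7 days (Day 1 to Day 8) or 14 days (Day 1 to Day 15), Protocol Table 3.
- Half-life 2.6 days: Table 5 predicts AUC0-168h 325 and Cmax 4.3 for 15 mg IV. Solving (1 − e^(−168k))/k = 325/4.3 = 75.6 h gives 2.57 days.
- Half-life 6.36 days: the Amendment 4 rationale equates the end-of-treatment visit with 5.5 half-lives; (57 − 22)/5.5 = 6.36.
- Absorption half-life (ta) is not given, so 0 to 3 days.

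**Formulas**, in units of IV AUCinf, with k = ln 2/half-life and ka = ln 2/ta, per day
- One-week IV share: w = 1 − e^(−7k)
- Carryover in the first SC week: c = e^(−k × gap) × w
- SC part: S = 0.75 × k × ka/(ka − k) × [(1 − e^(−7k))/k − (1 − e^(−7ka))/ka]; for ta = 0, S = 0.75w
- SAP formula: S + c
- Matched one-week ratio, AUCtau_corrected/AUC168h: S/w

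**Numbers put in**
- 2.6 days: w = 0.845. Carryover is 0.155 × 0.845 = 0.131 (7-day gap) or 0.024 × 0.845 = 0.020 (14-day gap).
- 6.36 days: w = 0.534. Carryover is 0.466 × 0.534 = 0.249 or 0.217 × 0.534 = 0.116.

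| Half-life (d) | ta (d) | S | SAP formula, subsequent | SAP formula, first | Gap | S/w |
|---|---|---|---|---|---|---|
| 2.6 | 0 | 0.634 | 0.765 | 0.654 | 14.5% | 0.750 |
| 2.6 | 1 | 0.565 | 0.696 | 0.585 | 15.9% | 0.669 |
| 2.6 | 2 | 0.468 | 0.599 | 0.488 | 18.5% | 0.554 |
| 2.6 | 3 | 0.388 | 0.519 | 0.408 | 21.3% | 0.459 |
| 6.36 | 0 | 0.400 | 0.649 | 0.516 | 20.5% | 0.750 |
| 6.36 | 1 | 0.336 | 0.585 | 0.452 | 22.7% | 0.630 |
| 6.36 | 2 | 0.270 | 0.519 | 0.386 | 25.6% | 0.506 |
| 6.36 | 3 | 0.221 | 0.470 | 0.337 | 28.3% | 0.414 |

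At a 1-day half-life the gap is 1.0% to 1.4%.

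**Changing only one term.** AUCtau_corrected over AUCinf equals S, which is below the SAP reading in every row. Uncorrected AUCtau over AUC168h is (S + c)/w. At 6.36 days and ta 0 that is 0.649/0.534 = 1.22 in subsequent participants.

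**Extrapolation.** The IV area beyond the last sample before SC dose 1 is e^(−k × gap): 15% and 2% at 2.6 days (subsequent, first), 47% and 22% at 6.36 days. The 20% limit is met at about 3.0 days or less (subsequent) and 6.0 days or less (first).

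**Pooling.** One first participant with four subsequent lowers the geometric mean by 3% to 5% at 2.6 days and 4% to 6% at 6.36 days. At the minimum of three per cohort (one with two), the figures are 5% to 8% and 7% to 11%.

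**The case against.** The strongest reply has four parts.

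*The endpoint does not fix the IV metric.* This stands. A reader might infer that the SAP contradicts its endpoint. The endpoint text names AUCtau for SC and leaves the IV side open, and Protocol 9.4 calls itself a high-level summary, so AUCinf can be read as a specification. The defect is in the formula.

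*The sponsor foresaw carryover, so AUCtau may mean the corrected value.* The first half stands. The SAP nowhere says in words that F is uncorrected. But it lists AUCtau and AUCtau_corrected as separate parameters and F names the former, so an analyst following the text leaves carryover in.

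*The errors largely cancel where AUCinf is reportable.* This stands in part. At half-lives of 3 days or less, subsequent participants read 0.69 to 0.77 for ta up to 1 day. In that range of half-lives the matched one-week ratio is further from 0.75 than the SAP formula for nearly all absorption rates (0.669 against 0.696 at 2.6 days, ta 1 day). At 6.36 days this happens only once ta exceeds about 1.8 days. The cancellation does not carry over to first participants, who read 0.585 in the same 2.6-day case, and it depends on kinetics not known when the SAP was written.

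*The consequence is small.* There are no hypotheses, the sample size is empiric, and AUC168h and any AUCtau_corrected are listed, so a reader could recompute. That limits the severity. A ratio chosen after the data are seen would still be unplanned.

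**Conclusion.** The concern holds as an unsound formula. F as written mixes carryover and truncation, and the result depends on the dosing gap. A reader might infer that F is overstated; the sign is not fixed, and in most of the cases shown the reading is below 0.75. A reader might also infer that the matched one-week ratio is always nearer the truth; it is not.

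The first-versus-subsequent gap is about 1% at a 1-day half-life, 14% to 21% at 2.6 days and 20% to 28% at 6.36 days. All sizes rest on one-compartment linear kinetics, true F 0.75 and an absorption half-life of 0 to 3 days. Neither half-life is a human measurement: one is a single-exponential fit to predicted values, and the other is inferred from an amendment rationale. The textual finding, that neither AUCtau_corrected nor AUC168h is linked to F, needs none of these assumptions. It should be fixed, but it touches no hypothesis test.

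**What to change.** In SAP 8.3 and 8.4:

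- Define the 168-hour comparison as AUCtau_corrected (SC dose 1)/AUC168h (IV), changing numerator and denominator together.
- Write the subtraction: AUCtau_corrected = AUCtau (SC dose 1) − C(predose SC dose 1) × [1 − e^(−λz × 168 h)]/λz. Name the source of λz (for example, each participant's terminal phase after SC dose 3), and apply it to everyone with a quantifiable SC dose 1 predose value.
- Label the result a one-week relative exposure that removes the carryover gap under constant clearance but understates F when absorption is slow. Do not claim that it is always closer to the true F.
- If the AUCinf-based F is kept as supportive, say that the 20% extrapolation rule applies to F and to the ANOVA, and show first and subsequent participants separately.

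A joint IV/SC model or a full-exposure estimate is optional.

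The cost is SAP wording and PK programming. The ratio may read low if absorption is slow (0.459 at 2.6 days, ta 3 days), and it depends on stable clearance. For example, at 6.36 days (k = 0.109), if clearance and so the later λz doubled from SC dose 2, the area subtracted in subsequent participants would be 0.466 × 0.783/0.218 = 1.67 instead of 0.466 × 0.534/0.109 = 2.28. Over AUC168h of 0.534/0.109 = 4.90, that raises the ratio by 0.12. The rise in first participants would be 0.06, so part of the gap would return.

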9.4.3. Other Analyses

9.4.3.1. Pharmacokinetic Analyses

All PK analyses will be performed on the PK Set and will be reported by each cohort. The individual plasma concentration data from participants who receive ALXN1850 with actual sampling dates and times will be used to derive the PK parameters by noncompartmental analyses methods using Phoenix WinNonlin 8 or higher.

PK Parameters	Definition
C _{max}	Maximum observed plasma concentration
t _{max}	Time to maximum observed plasma concentration
AUCt	Area under the plasma concentration versus time curve from time 0 to the last quantifiable concentration
AUC _{tau}	Area under the plasma concentration versus time curve during the dosing interval
AUC _∞	Area under the plasma concentration versus time curve from time 0 (dosing) to time infinity
t _{1/2}	Terminal elimination half-life
λ _z	Terminal-phase elimination rate constant
CL or CL/F	Total body clearance
Vd or Vd/F	Volume of distribution
R	Subcutaneous accumulation ratio (Dose 3/Dose 1)
F	Absolute bioavailability after subcutaneous administration

The following PK parameters will be derived:

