Study participants will be enrolled into 3 cohorts in a sequential fashion. The first participant in each cohort will begin dosing before the rest participants of the cohort. A Safety Review Committee (SRC) will convene after the first participant in each cohort has completed the first IV dose to assess safety and tolerability, and to endorse initiation of SC study drug administration to the first participant as well as IV and SC study drug administration to the remaining number of participants in the cohort. Once at least 3 participants in Cohort 1 participants have received a single IV dose and 3 weekly SC doses, the SRC will convene again to review safety and tolerability data, and to determine if the dose escalation may proceed. If the SRC endorses dose escalation, Cohort 2 will begin dosing at the next dosing level. Cohort 3 will begin dosing after the SRC has reviewed all relevant safety, tolerability, and PK data from participants in Cohorts 1 and 2 and endorsed dose escalation. The study design is presented in Figure 1.

Participants who are positive for ADAs at the last assessment of the study will be given options to enable further monitoring of their ADA values after the end of the study; these options may include enrollment in the Global HPP Registry.

4. General Statistical Considerations

All statistical analyses will be conducted using statistical analysis system SAS® Version 9.4 or higher (SAS Institute, Inc., Cary, North Carolina) and Phoenix® WinNonlin® Version 8.0 or higher (Certara USA, Inc., Princeton, New Jersey).

Descriptive statistics for continuous variables will include number of participants (N), number of non-missing values (n), a rithmetic mean, geometric mean (for PK analysis only), standard deviation (SD), pe rcent coefficient of variation (%CV; for PK analysis only), geometric %CV (for PK analysis only), median, quartile 1 (Q1, for safety analysis only), quartile 3 (Q3, for safety analysis only), i nterquartile range (IQR, for safety analysis only), minimum, and maximum, unless otherwise noted. For categorical variables, frequencies and percentages will be presented. Descriptive statistics will be summarized by cohort and overall and by timepoint, unless otherwise noted. In the case where N is an even number, the median will be calculated as the average of the 2 middle numbers of the ordered samples or parameter estimates.

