For the summary statistics of all continuous variables unless otherwise specified, for absolute value, minimum and maximum will be presented to the same number of decimal places as the raw data, mean, median, Q1, Q3, and IQR will be presented to one more decimal places than the raw data, SD will be presented to two more decimal places than the raw data; for percent change, minimum and maximum will be presented to one decimal place, mean, median, Q1, Q3, and IQR will be presented to two decimal places, and SD will be presented to three decimal places. %CV and geometric %CV will be presented to one decimal place, and N and n will be presented to integer.

Percentages will be suppressed when the count is zero and will be presented to one decimal place. The denominator for all percentages will be the number of participants in the cohort for the population of interest, unless otherwise specified.

All tables, listings, and figures will be presented by cohort, unless otherwise specified.

All data listings will be sorted by cohort, participant number, and date-time if applicable.

No algorithm for imputation of missing data will be employed but will be analyzed as missing.

Study days are calculated with respect to the first dose date as below:

- If the assessment/observation date is on or after the first dose date, then Study Day = Assessment/Observation Date First Dose Date + 1;
- Otherwise, Study Day = Assessment/Observation Date First Dose Date

Study weeks are calculated with respect to the first dose for the assessment/observation occurred on or after the first dose as below, unless otherwise specified:

• Study Week = Integer part of (Assessment/Observation Date – First Dose Date)÷7+1

Baseline will be defined as the last non-missing assessment (including repeated and unscheduled assessments) before the first dose of study drug administration, unless otherwise specified.

For summary of safety assessments, if there are repeated measurements at a time point, the first non-missing assessment at that time point will be used in the summary tables.

Unscheduled results will not be included in the summary tables, except for determining Baseline, but will be presented in data listings.

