In addition to the above PK parameters, which will be listed and summarized, the following parameters will also be listed to document the selection of data points used to estimate $T_{1/2}$ using non-compartmental procedures:

λ_z	Terminal phase elimination rate constant
Number points	Number of data points used to estimate λ_z ; a minimum of 3 data points must be used, and C_{max} must not be included
λ_z lower	Lower bound used for the estimation of λ_z
λ_z upper	Upper bound used for the estimation of λ_z
Rsq	r^2 , the coefficient of determination (goodness of fit statistic); λ_z and all associated parameters will only be reported where $r^2 \ge 0.80$
%AUC _{extrap}	Percentage of AUC_{inf} due to extrapolation; If % $AUC_{extrap} > 20\%$ then, AUC_{inf} , CL, and V_d , will not be summarized

Additional plasma PK parameters may be calculated if deemed appropriate.

Plasma PK parameters for ALXN1850 will be presented in data listings and summarized separately using descriptive statistics (n, arithmetic mean, SD, %CV, geometric mean, geometric %CV, median, minimum, and maximum) by treatment. T_{max} will be summarized using the descriptive statistics median, minimum, and maximum only. Plasma PK will be presented by ADA status in figures. In addition, the Plasma PK parameters and ADA titers will be presented in the overlay figures for each subject overtime.

Plasma PK parameters of ALXN1850 will be reported to 3 significant figures in summary statistics except for %CV which will be reported to 1 decimal place and N and n which will be reported as integers.

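### SAP 8.4 does not say whether bioavailability is estimated per cohort or over all cohorts, and names no all-cohort estimate with a confidence interval

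*SAP*

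**What the plan says.** Protocol section 3 (Table 4) lists as a secondary objective "Assess the absolute bioavailability of ALXN1850 SC", once and without reference to dose. Each participant is scheduled to receive one IV dose and three SC doses at the same mg level: 15, 45 or 90 mg (protocol 4.3).

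SAP 8.4 compares AUC_tau "values of the first SC dose versus AUC_{inf} of the IV dose for the similar dose" cohorts (the phrase runs over a page break). The log-transformed areas are "analyzed using an analysis of variance model with group (IV vs SC) as a factor", and "the ratio of geometric means and 90% CIs will be presented". The analysis is then repeated by ADA status. The section does not say whether the ANOVA is fitted within each cohort or across them. It names no term for cohort, dose or participant.

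Four other statements bear on the reading:

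- Protocol 9.4.3.1: "All PK analyses will be performed on the PK Set and will be reported by each cohort".
- SAP section 4: "All tables, listings, and figures will be presented by cohort, unless otherwise specified".
- SAP section 4, for descriptive statistics: "Descriptive statistics will be summarized by cohort and overall and by timepoint, unless otherwise noted".
- SAP 8.3, where individual F is a listed parameter, summarises parameters by "geometric mean, geometric %CV, median, minimum, and maximum) by treatment".

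**The concern.** The objective asks for one quantity, and the IV dose is in the design to provide the reference for it (protocol 4.2). Because each participant has both routes at the same dose, the SC/IV ratios could be combined across cohorts.

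Neither reading of SAP 8.4 does this well. Read per cohort, the result is three intervals from 3 to 5 participants each. The repeat by ADA status thins them further: a cell with one participant leaves 2×1 − 2 = 0 residual degrees of freedom and no interval. Read as a single ANOVA with route alone, the spread of AUC between 15 and 90 mg is counted as error.

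At stake is the precision with which a stated secondary objective is reported, and whether the all-cohort estimate is fixed in advance or chosen after the data are seen.

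**Working it through.** The documents give no precision target, CV or confidence-interval width for F, and call the sample size empiric (SAP 4.2). The only figures to reproduce are the counts: 3 × 5 = 15 enrolled and 3 × 3 = 9 completing. Both match.

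**Inputs.** n = 3 to 5 per cohort (protocol 1.1, SAP 4.2); 90% two-sided intervals (SAP 8.4); doses 15, 45 and 90 mg (protocol 4.3). Assumed, because the documents do not give it: σ, the SD of ln(AUC) within a route and cohort, from a CV of 20% to 50%. Also assumed: s, the SD of the within-participant ln(AUC_SC/AUC_IV), 0.2 to 0.4. Width ratios on the log scale do not depend on σ or s if they are equal across cohorts.

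**1. Unpaired, as the SAP names the model.** Half-widths in units of σ:

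- Per cohort, t(0.95; 2n−2)·√(2/n). n=3: 2.132 × 0.816 = 1.741. n=5: 1.860 × 0.632 = 1.176.
- All cohorts, cohort + route, t(0.95; 6n−4)·√(2/(3n)). 9 participants: 1.761 × 0.471 = 0.830. 15 participants: 1.706 × 0.365 = 0.623.
- Ratios: 1.741/0.830 = 2.10 and 1.176/0.623 = 1.89. Of this, √3 = 1.73 comes from sample size and the rest from degrees of freedom.

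At a 30% CV, σ = √ln(1.09) = 0.294. The limits as multiples of the estimate are:

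| n per cohort | Per cohort | All cohorts, cohort + route |
|---|---|---|
| 3 | 0.60 to 1.67 | 0.78 to 1.28 |
| 5 | 0.71 to 1.41 | 0.83 to 1.20 |

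**2. Paired in both.** Half-widths in units of s:

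- Per cohort, t(0.95; n−1)/√n. n=3: 2.920/1.732 = 1.686. n=5: 2.132/2.236 = 0.953.
- All cohorts, participant + route, t(0.95; 3n−1)/√(3n). 9 participants: 1.860/3 = 0.620. 15 participants: 1.761/3.873 = 0.455.
- Ratios: 1.686/0.620 = 2.72 and 0.953/0.455 = 2.10.
- With route-by-cohort also in the model the degrees of freedom fall to 6 and 12, and the half-widths become 0.648 and 0.460.

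Over s = 0.2 to 0.4, the all-cohort limits are exp(0.620s) = ×/÷1.13 to 1.28 with 9 participants and exp(0.455s) = ×/÷1.10 to 1.20 with 15.

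**3. One ANOVA over all cohorts with route only.** Assume AUC proportional to dose. The logs of 15, 45 and 90 are 2.708, 3.807 and 4.500, with squared deviations from their mean summing to 1.633. With 15 participants and two routes this adds 2 × 5 × 1.633/28 = 0.583 to the residual variance. At a 30% CV the total is 0.583 + 0.086 = 0.669. The half-width is 1.701 × √(2 × 0.669/15) = 0.508, so the limits are ×/÷1.66. One cohort of 5 gives 1.176 × 0.294 = 0.345, or ×/÷1.41.

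The comparison depends on the CV. For n=5 per cohort, the route-only and per-cohort half-widths are 0.490 and 0.233 at 20%, 0.531 and 0.453 at 40%, and 0.558 and 0.556 at 50%. At 50% with n=3 the order reverses (0.752 and 0.822). At every CV checked, the cohort-plus-route model is narrower than both.

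**The case against.** A reader might infer that the SAP orders three separate ANOVAs and rules out any overall F. The text does not go that far. The phrase about similar dose cohorts could mean only that doses are matched. By-cohort fitting is the best reading, because of protocol 9.4.3.1 and the SAP section 4 presentation default, but it is not stated. An overall descriptive F is not clearly excluded either: SAP section 4 has descriptive statistics by cohort and overall, while SAP 8.3 says by treatment. Such a summary would carry no planned interval, although a reader could build one from its n, geometric mean and geometric %CV.

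The sponsor can also say that by-cohort results suit a dose-escalation study and follow the protocol. No hypotheses are planned (SAP 4.1), and no escalation criterion in protocol 6.6.1 uses F. All of that stands and limits the weight of the point. It might further be inferred that side-by-side intervals will be read as dose-dependent bioavailability, but no SAP step draws that conclusion. The across-dose power models in SAP 8.4 bear on the question, though they yield slopes by route and not F.

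The strongest statistical objection is that combining assumes the same F and similar variance at all three doses. The documents do not establish this. The single 75% SC bioavailability in the starting-dose calculation (protocol 4.3) is a planning assumption, not evidence. A route-by-cohort test on 6 to 12 residual degrees of freedom can check it only weakly. First participants also receive SC dose 1 on Day 15 and the others on Day 8, and SAP 8.2 summarises their concentrations separately after Day 8, combining them only in a carryover-corrected sensitivity analysis. These are reasons to keep the by-cohort ratios alongside a combined estimate, not reasons to leave the combined estimate out.

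**Conclusion.** The point holds as an unclear specification and a missing additional estimate. SAP 8.4 leaves the fitting unit open and names no all-cohort F with an interval. Under the per-cohort reading, the log-scale interval is 1.9 to 2.1 times as wide as a combined unpaired one, or 2.1 to 2.7 times when both are paired. This rests on equal variance and a common F. Under the single-ANOVA reading at a 30% CV, the interval is wider than within one cohort, and the comparison narrows as the CV rises.

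Two stronger conclusions are not supported. The by-cohort ratios are not wrong. Nor is a factor of two the gap to what the data allow: with within-participant correlation ρ, the unpaired by-cohort interval is 1.8 to 2.0 times the combined paired one at ρ = 0, 2.6 to 2.8 times at 0.5 and 4.1 to 4.4 times at 0.8. The documents give no ρ.

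Combining does not cure the comparison of an SC area over one dosing interval with an IV area extrapolated to infinity. The SAP 8.3 rule against summarising AUC_inf when extrapolation exceeds 20% may also reduce the usable n. This is a cheap improvement, and no trial decision turns on it.

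**What to change.** In SAP 8.4, state that the SC/IV ratios are estimated within each cohort and kept. Add one prespecified model over all cohorts, ln(AUC) = participant + route. Participant absorbs cohort and dose, so neither needs its own main effect. Report one geometric mean ratio SC/IV with its 90% CI as the combined estimate of F. Show route-by-cohort descriptively, labelled as a low-power check. Use the carryover-corrected AUC_tau already defined in SAP 8.3 where IV carryover is observed, and state how many participants contribute.

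The cost is one model and one table row, with no new data. The downside is the assumption of a common F across 15, 45 and 90 mg and across first and subsequent participants, which the retained by-cohort ratios let the reader judge. The AUC_tau/AUC_inf mismatch needs its own resolution.
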